4. TREATMENT PLAN

4.1 Dose of INCB018424 and Treatment Cycle

This is a phase II study of oral INCB018424 in patients with relapsed/refractory AML, ALL, and MDS (including CMML), and blast phase or tyrosine kinase refractory CML. The starting dose of INCB018424 will be 25 mg po twice daily, which has been determined to be the maximum tolerated dose in patients with myelofibrosis with myeloid metaplasia and a dose that is tolerated for ten days in normal human volunteers.

INCB018424 will be administered orally at a dose of 25 mg BID for 7 days each week for 4 weeks (cycle number 1). Patients will be evaluated after 1 full cycle of therapy (28 days) for response. Responding patients or patients with stable disease will be allowed to continue on study at a dose of 25 mg INCB018424 BID until progression. The response assessment for the purpose of study statistical evaluation will be after two cycles (8 weeks) of therapy. Patients with progressive disease, based on clinical and laboratory evaluation, will, at the discretion of the Investigator, either be removed from the study or, as long as the 25 mg BID dose has been well tolerated, dose escalated to 50 mg INCB018424 BID. In instances of dose escalation to 50mg BID, patients will be evaluated after

1 full cycle of therapy (28 days) for response and toxicity. At that point, patients with continued progressive disease, based on clinical and laboratory evaluation, will be removed from the study. In instances of dose escalation, the response assessment for the purpose of study statistical evaluation will be after two cycles (8 weeks) of therapy at the 50 mg BID dose.

Patients with chronic phase CML who have failed at least 2 prior tyrosine kinase inhibitors and do not have a standard transplant option will be assessed for response after 3 months of therapy in the absence of loss of disease control and they may continue therapy if they demonstrate any clinical benefit. Patients with chronic phase CML will not be allowed to have the dose escalation as this population has less of a life-threatening disease situation.

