4.2 Administration of INCB018424

This is an open label, non-randomized, study of INCB018424, administered orally to patients with relapsed/refractory AML, ALL, and MDS (including CMML), and blast phase or tyrosine kinase refractory CML. The study of INCB018424 in each disease listed will be conducted in two parts. The first part is intended to enroll a maximum of 10 patients within each of the four disease categories included in this study and to identify whether significant benefit is observed. If a minimum of one patient shows benefit that is considered significant, there will be an expanded cohort of 20 additional patients treated in that arm of the study.

Patients will receive 50 mg/day administered orally in two divided doses (i.e., BID: every 12 hours \pm 2 hours). Within each arm of the study, three patients will be initially treated and observed for toxicity for one treatment cycle (28 days) before the additional seven patients are entered. Dose reduction will be considered if the number of patients experiencing grade 3 or higher toxicities exceed 2/3, 3/4, 4/7, 5/10, 6/14, 7/18, 8/22, 9/26. Treatment will be administered primarily on an outpatient basis, but can be administered as an inpatient if the patient is hospitalized for other reasons.

The 5 mg tablets have been shown to be stable when stored up to one month at 25° C/60%RH and 40° C/75%RH; the 25 mg tablets have been shown to be stable when stored for three months at 25° /60%RH and 40° /75%RH. (25° C = 77° F, 40° C = 104° F).

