4.4 Duration of Therapy

In the absence of treatment delays due to adverse event(s), treatment may continue until one of the following criteria applies:

- Lack of objective response after 2 cycles of therapy (3 cycles if there is dose escalation to 50 mg BID after cycle 1) unless INCB018424 is considered to be of clinical benefit to the patient
- Intercurrent illness that prevents further administration of treatment
- Unacceptable adverse event(s)
- Patient decides to withdraw from the study, or
- General or specific changes in the patient's condition render the patient unacceptable for further treatment in the judgment of the investigator.

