5.2 Study Procedures

•	Screening Phase	Treatment Phase								End of Treatment		
Visit	Day -28 to Day -1	Cycle 1			Cycle 2+3			Subsequent Visits - For details see Footnotes		1		
		Day 1	Day 8	Day 15	Day 22	Day 1	Day 8	Day 15	Day 22	Day 1	Day 15	End of Study ^o
Evaluation – All evaluations have a												•
+/- 2 day window except for bone												
marrow biopsy (see footnote i).												
Informed consent ^a / Eligibility criteria	X	X										
Medical & medication history ^b	X	X	X	X	X	X				X ^b		X
Physical examination ^c	X	X	X	X	X	X				X ^c		X
Vital signs ^c	X	X	X	X	X	X				X ^c		X
Overall Response assessment (IWG-MRT) ^d						X				X ^d		X
ECOG performance status ^e	X					X				Xe		X
Concomitant medication review ^f		X	X	X	X	X				X ^f		X
Clinical laboratory tests ^g	X		X	X	X	X		X		X ^g		X
CBC ^h	X		X	X	X	X	X	X	X	X ^h	X^h	X
PT/PTT	X											
CXR	X											
Pregnancy test ^g	X											
FSH test ^g	X											
Serology / HIV laboratory tests ^g	X											
Urinalysis ^g	X											
BM aspiration, biopsy and cytogenetics ⁱ	X									Xi		
Administer 1st dose of INCB018424 ^j		X										
Dispense INCB018424 study medication ^j		X				X				X ^j		
PK sampling ^k		X				X						
PD biomarker sampling ¹		X				X				X ¹		X
Adverse event / Intercurrent illness assessment ^m		X	X	X	X	X				X ^m		X
Study medication compliance ⁿ			X	X	X	X				X ⁿ		X

- a. Informed consent must be obtained at Screening. At Screening and Day 1, assess eligibility for study entry and review eligibility for study entry on Day 1.
- b. Medical history will be done at each visit. Medication history will be obtained only at the screening visit.
- c. A complete examination will be performed at Screening and the End-of-Study Visit . A "targeted" examination will be performed at all other visits. During the treatment phase, weekly visits at the local physician's office are required during 1st cycle of therapy with a review of constitutional symptoms and physical exam, including transfusion requirement. During 2nd and 3rd cycles visits are every 4 weeks, and then every 3 months thereafter. All examinations will include body weight. On Day 1 of Cycle 1, before PK/PD blood-draws, the vital signs will be done as well as with the physical exams. On all other clinical visits vital signs are taken once. Overall response assessments will be graded according to consensus criteria for treatment response.

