- d. Overall response assessments are required on Day 1 of Cycles 2, 3, and 4 and then every 3 months thereafter. If the dose of INCB018424 is escalated to 50 mg BID after cycle 1, then overall response assessments are required on Day 1 of Cycles 3, 4, and 5 and then every 3 months thereafter.
- e. ECOG performance criteria must be 0, 1 or 2 at screening. ECOG assessment is required on Day 1 of 2nd and 3rd cycles and thereafter every scheduled subsequent visit on Day 1.
- f. All medications received within 30 days prior to the Screening Visit are to be recorded. Reassessments will be done weekly at the local physician's office during 1st cycle of therapy and then every 4 weeks during 2nd and 3rd cycles and thereafter every 3 months during scheduled visits.
- g. Serum chemistry (Sodium, potassium, chloride, CO₂, blood urea nitrogen, creatinine, glucose, calcium, phosphate, magnesium, AST or ALT, total bilirubin, alkaline phosphatase, total protein, albumin, uric acid, lactic dehydrogenase) is required every week during the 1st cycle and every two weeks during Cycles 2 and 3, and at each scheduled subsequent visit. Urinalysis is required only at screening and at the end of study visit. Hepatitis serology and HIV laboratory test will be performed only during the Screening Visit if there are no results available from past 3 months. A pregnancy test will be obtained at screening. Urine pregnancy test will then be performed if there is a suspicion of pregnancy. A serum pregnancy test will be performed to confirm positive results obtained from a urine test. FSH test will only be performed on females who have been amenorrheic for >1 year, and if levels are elevated no further pregnancy testing is required for these female patients.
- h. Complete blood count (CBC) including absolute neutrophil count and platelet count are required weekly for Cycle 1, 2 and 3 and every two weeks for subsequent visits.

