- i. Bone marrow aspiration or biopsy will be taken during the screening phase (within 4 weeks of starting drug), and at start of Cycle 4 (± 7 days), Cycle 7 (± 7 days), and thereafter at start of each 6th subsequent cycle (+/- 7days). Evaluation will include staining for fibrosis and cytogenetics if abnormal prior to therapy. Cytogenetic studies will be repeated only in patients with abnormalities at baseline, on Day 1 of Cycles 4 and 7 and thereafter on Day 1 of each 6th subsequent cycle(+/-7days). If unable to obtain BM aspirate, cytogenetics may also be done on peripheral blood collected for PD/PK analysis.
- j. Instruct patient that the dose is to be taken at 12 hour intervals at approximately the same time each day. The first dose of each day should be taken in the morning.
- k. For Cycle 1, PK samples to be collected on Day 1 at pre-dose, 0.5, 1, 1.5, 2, 4, 6, and if possible 8 hours after administration of the morning dose of INCB018424. For Cycles 2 and 3, a PK sample will be collected at pre-dose on Day 1.
- I. For Cycle 1, plasma and whole blood PD samples will be collected on Day 1 at pre-dose and 2, hours after administration of the morning dose of INCB018424. For Cycles 2, 3, and each subsequent scheduled visit to MDACC, plasma and whole blood PD samples will be collected at pre-dose on Day 1. Final PD sample will be collected at End-Of–Study visit. Not all samples may be collected on all patients. See Appendix F.
- m. Adverse events (AEs) considered related to study medication must be followed until resolution, start of a different treatment therapy or no longer considered to be clinically relevant in the opinion of the investigator. During the treatment phase, AE assessment is required weekly at the local physician's office during 1st cycle of therapy. During the 2nd and 3rd cycles assessments are required every 4 weeks, and then every visit thereafter.
- n. Compliance should be checked at each scheduled clinical visit. Any unused drug in sealed bottles will be returned to Incyte or its designee. MDACC will follow internal procedures to destroy and dispose of unused drug in open/unsealed bottles.

Protocol Number 2007-0925 October 13, 2008 Page 17 of 36

o. End-of-Study procedures are to be completed if patient completes study or at anytime patient terminates treatment early in the study.

5.2.1 Cycle 1

5.2.1.1 Cycle 1 - Day 1

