5.2.2.1 Day 1 ± 2 days

The following procedures will be performed:

- Review of medical history and concomitant medication.
- Review of any adverse events.
- Targeted physical examination and vital signs.
- ECOG performance status.
- Urine collection for pregnancy test on females of childbearing potential only.
 If positive then serum pregnancy test will be done.
- Blood sampling for the following:
 - → Blood serum chemistry tests, CBC with Differential, ANC, platelet count
 - o PK analysis sample collection pre-dose
 - Plasma and whole blood PD marker analysis sample collection predose
- Overall response assessment.
- Administration of the morning dose of INCB018424.
- A study medication tablet count will be done to assess compliance. If patient qualifies for continued dosing, they will be provided with study medication for the next 4 weeks.
- Patients will be asked to return to the clinic on Day 1 of Cycle 3 (Day 28 of Cycle 2 ± 2 days). Patients will be asked to bring all study medication with them to the visit.
- Due to PK and PD samples being collected at the next visit, patients will be asked to withhold their morning dose of study medication on Day 1 of Cycle 3.
- All procedures listed above, including dispensing of study medication for next 4 weeks of Cycle 3, if patient qualifies for continued dosing, will be performed on Day 1 of Cycle 3 ± 2 days. Patients will be asked to return to the clinic on Day 1 of Cycle 4 (Day 28 of Cycle 3 ± 2 days). Patients will be asked to bring all study medication with them to the visit.
- Due to PD samples being collected at the next visit, patients will be asked to withhold their morning dose of study medication on Day 1 of Cycle 4.

- Review all safety information and criteria for dosing interruptions to determine if patients should receive further doses.
- Patients will be instructed to call the Investigator or designated research staff if they experience any "troubling" signs and/or symptoms that are of moderate or greater severity.

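### For starting-dose patients outside chronic-phase CML, the 8-week statistical response read has no scheduled marrow; the first on-treatment marrow comes nominally 28 days later

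*Combined protocol and SAP*

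**What the plan says.** **The read.** Section 4.1 states: "The response assessment for the purpose of study statistical evaluation will be after two cycles (8 weeks) of therapy". If the dose is escalated, the read is after two cycles at the higher dose. Chronic-phase CML is read after three months. Section 5.2, footnote d, adds for patients without escalation: "Overall response assessments are required on Day 1 of Cycles 2, 3, and 4 and then every 3 months thereafter".

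**The marrow.** Footnote i states: "Bone marrow aspiration or biopsy will be taken during the screening phase (within 4 weeks of starting drug), and at start of Cycle 4". It then lists Cycle 7 and every sixth cycle after that, each ± 7 days. Sections 5.2.3 and 7.3 agree, and Section 7.3.2 gives the same timing for repeat cytogenetics. The calendar's marrow row is marked only at Screening and under Subsequent Visits. The Day 1 list for Cycles 2 and 3 (5.2.2.1) has an overall response assessment but no marrow. The End-of-Study visit (5.2.5) is built on that list.

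**The response categories.** Section 6.1 defines complete remission by a marrow differential, CRp as complete remission apart from platelets, and partial remission by abnormal marrow cells or a fall in marrow blasts. Only hematologic improvement rests on blood counts and transfusions.

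**What depends on it.** Section 9.1.1 expands an arm on at least one response in 10 patients and names no time point. Section 4.2 puts the same step as: "If a minimum of one patient shows benefit that is considered significant". Section 4.4 lists as an end-of-treatment criterion: "Lack of objective response after 2 cycles of therapy (3 cycles if there is dose escalation to 50 mg BID after cycle 1) unless" the drug is judged to be of clinical benefit to the patient.

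**The concern.** Anti-tumor effect is the primary objective, and a single response decides whether an arm grows from 10 to 30 patients. On the main treatment path the plan fixes the statistical read at a visit where the information that defines response has not been scheduled. Someone following the calendar exactly could not assign complete remission, CRp or partial remission at that read. The two-cycle criterion in Section 4.4 is likewise judged before any scheduled on-treatment marrow, and a patient who leaves then has none at the End-of-Study visit either. Section 9.2.1 also asks for response estimates at each time point, yet of the first three scheduled assessments (Day 1 of Cycles 2, 3 and 4) only the third has a marrow.

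**Working it through.** **The plan's own figures reproduce.** Two cycles: 2 × 28 = 56 days = 8 weeks. Chance of at least one response in 10 at a true rate of 15%: 1 − 0.85^10 = 0.803, against a stated 80%. Half-width at n = 30: 1.96 × √(0.15 × 0.85 / 30) = 0.128, against 0.13. Total: 4 × 30 = 120. The sample size is not in question.

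**Dates.** With 28-day cycles (Section 6), Day 1 of cycle c is 28(c − 1) + 1:
- end of Cycle 2 = Day 56; Cycle 3 Day 1 = Day 57
- Cycle 4 Day 1 = Day 85, so the marrow window is 85 ± 7 = Day 78 to 92
- Cycle 7 Day 1 = Day 169

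Nominal gap: 85 − 57 = 28 days.

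**Windows.** The documents give three windows for the read. In the calendar, marrow is exempt from the ± 2 days ("2 day window except for bone") and has its own ± 7. Section 5.2.2.1 anchors the visit one day earlier than the calendar: "return to the clinic on Day 1 of Cycle 3 (Day 28 of Cycle 2 ± 2 days").

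| Source of read window | Read | Smallest gap | Largest gap |
|---|---|---|---|
| Section 6, end of cycle ± 4 | Day 52–60 | 78 − 60 = 18 | 92 − 52 = 40 |
| 5.2.2.1, Day 28 of Cycle 2 ± 2 | Day 54–58 | 78 − 58 = 20 | 92 − 54 = 38 |
| Calendar, Cycle 3 Day 1 ± 2 | Day 55–59 | 78 − 59 = 19 | 92 − 55 = 37 |

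The read and marrow windows never overlap.

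**Who is outside the problem.** A patient escalated after cycle 1 starts the higher dose on Day 29 and reaches eight weeks at the end of Day 84 (28 + 56), next to the Cycle 4 marrow on Day 85. Chronic-phase CML, read at three months, also falls at about Cycle 4. Both line up.

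**Blast-phase CML.** Section 6.1 covers it by its heading. Scoring it under Section 6.2 would not help: complete and minor hematologic response there also use marrow blasts.

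**Reach.** AML, ALL and MDS are whole arms: 3 × 10 = 30 of 40 first-stage patients and 3 × 30 = 90 of 120 in all, plus an unstated number of blast-phase patients in the CML arm. For the three arms these are upper bounds on patients under the mismatched schedule, because those escalated or removed after cycle 1 drop out of the count and their share is not given.

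**The case against.** Several provisions soften the consequence, and all of them stand.

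- **A later response may count.** Section 9.1.1 ties the 1-in-10 rule to no date, Section 4.2 speaks only of significant benefit, and Section 4.1 says "Responding patients or patients with stable disease will be allowed to continue on study". A stable patient can reach the Cycle 4 marrow and be documented then.
- **The two-cycle criterion is not absolute.** Section 4.4 exempts a patient for whom the drug is considered of clinical benefit.
- **An unscheduled marrow is not forbidden.** An investigator who suspects a response at eight weeks may obtain one, and Section 9.5.2 requires patients to be assessed for response.
- **Efficacy is exploratory.** Section 9.2.1 says so.

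A reader might infer that responses cannot be counted at all, that the expansion rule cannot be met, or that power falls below the stated 80%. The documents support none of these. A response is lost only if it shows in the marrow alone, the patient leaves after two cycles, and no unscheduled marrow is taken. The documents give no rate for any of these steps, so any reduced power figure would be invented. Nor are 30 of 40 or 90 of 120 counts of lost responses.

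What the provisions do not do is make the stated read workable. They rely on discretion or on a later visit, whereas Section 4.1 names eight weeks as the read for statistical evaluation. In an open-label study, discretionary marrows would also make documentation depend on who is suspected of responding.

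**Conclusion.** The mismatch is real and consistent across Sections 4.1, 5.2, 5.2.2.1, 5.2.3, 6.1 and 7.3. For starting-dose patients with AML, ALL, MDS/CMML or blast-phase CML, the marrow-defined responses cannot be documented from scheduled data at the eight-week read. The first scheduled on-treatment marrow is nominally 28 days later and at least 18 days later under every stated window. This rests on 28-day cycles without delay and on the schedule as written.

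The practical harm is confined to marrow-only responses in patients who leave after two cycles without an unscheduled marrow. Its size cannot be estimated from the documents, and the 80.3% stands if all responses are documented. It should be fixed, because it concerns the primary outcome and the correction is cheap, but it does not invalidate the design. Whether hematologic improvement counts as a response (Sections 4.2, 9.1.1 and 9.5.2) is a separate question of definition that exists whatever the marrow timing.

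**What to change.** Make the statistical read and a scheduled marrow coincide for these patients.

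**Minimum fix, no extra procedure.** Restate the read in Section 4.1 as the response at the Cycle 4 marrow. Count a missing marrow as non-response for the marrow-defined categories. State in Section 9.1.1 that the 1-in-10 rule uses this read. Cost: the read comes four weeks later, and patients who leave early without a marrow count as non-responders.

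**Alternative, if the sponsor wants to keep eight weeks.** Schedule the first on-treatment marrow at Cycle 3 Day 1 for these patients and score the read on that marrow. Keep the Cycle 4 marrow for chronic-phase CML and for any patient whose dose is escalated, whenever that occurs. The last clause matters because Section 4.1 does not limit escalation to the end of cycle 1. A patient escalated after cycle 2 is read at about Day 57 + 56 = 113, and without the Cycle 4 marrow would have none between Day 57 and Day 169. Cost:
- patients who stop at eight weeks have a marrow they would not otherwise have had;
- a patient escalated after the Cycle 3 marrow has a second one at Cycle 4;
- other patients have no scheduled marrow from Day 57 to Day 169, so the interval grows from 169 − 85 = 84 to 169 − 57 = 112 days and a later response may be picked up late.

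Under either fix, reconcile Sections 4.1, 4.4, 5.2 (calendar, footnotes d and i), 5.2.2.1, 5.2.3, 5.2.5, 6, 7.3 and 7.3.2 with the chosen timing. Because 5.2.5 copies the 5.2.2.1 list, say whether the End-of-Study visit includes a marrow. No dose or stopping rule is proposed; the two-cycle criterion in Section 4.4 only has to be made consistent with when response can be determined.

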5.2.2.1 Day 1 ± 2 days

The following procedures will be performed:

- Review of medical history and concomitant medication.
- Review of any adverse events.
- Targeted physical examination and vital signs.
- ECOG performance status.
- Urine collection for pregnancy test on females of childbearing potential only.
 If positive then serum pregnancy test will be done.
- Blood sampling for the following:
 - → Blood serum chemistry tests, CBC with Differential, ANC, platelet count
 - o PK analysis sample collection pre-dose
 - Plasma and whole blood PD marker analysis sample collection predose
- Overall response assessment.
- Administration of the morning dose of INCB018424.
- A study medication tablet count will be done to assess compliance. If patient qualifies for continued dosing, they will be provided with study medication for the next 4 weeks.
- Patients will be asked to return to the clinic on Day 1 of Cycle 3 (Day 28 of Cycle 2 ± 2 days). Patients will be asked to bring all study medication with them to the visit.
- Due to PK and PD samples being collected at the next visit, patients will be asked to withhold their morning dose of study medication on Day 1 of Cycle 3.
- All procedures listed above, including dispensing of study medication for next 4 weeks of Cycle 3, if patient qualifies for continued dosing, will be performed on Day 1 of Cycle 3 ± 2 days. Patients will be asked to return to the clinic on Day 1 of Cycle 4 (Day 28 of Cycle 3 ± 2 days). Patients will be asked to bring all study medication with them to the visit.
- Due to PD samples being collected at the next visit, patients will be asked to withhold their morning dose of study medication on Day 1 of Cycle 4.

- Review all safety information and criteria for dosing interruptions to determine if patients should receive further doses.
- Patients will be instructed to call the Investigator or designated research staff if they experience any "troubling" signs and/or symptoms that are of moderate or greater severity.

